2. IDENTIFICATION AND DESCRIPTION OF THE INVESTIGATIONAL DEVICE

2.1. Investigational Devices

2.1.1. Lubricin

Lubricin, also called Proteoglycan 4 (PRG4), is a mucin-like glycoprotein originally discovered in synovial fluid, as a secreted product of cells that line the joint tissues, which is present at the surface of articular cartilage (1,2).

In vitro studies have shown that lubricin in saline buffer acts as a lubricant between various surfaces, as well as in synovial fluid, providing evidence that lubricin is a principal lubricating protein in joints. Besides the lubricating property, lubricin has been shown to exert anti-adhesive action, strain energy dissipation, anti-bacterial and a protective effect on underlying cells (3-6).

The lubricating, anti-adhesive, protective and anti-bacterial properties of Lubricin raised interest on its roles at the ocular surface, in normal and pathologic conditions such as dry eye (see **Lubricin Investigator's Brochure, CCI** [REDACTED] (7)).

The expression of Lubricin in animal models and in human ocular surface and meibomian gland was first described by the team of D. Sullivan (8,9).

As previously mentioned, lubricin has recently been discovered at the ocular surface, where its boundary lubricating properties may play a critical protective role as they do at the articular cartilage surface. Specifically, human corneal and conjunctival epithelial cells have been shown to express PRG4 mRNA, and PRG4 protein has been observed in human meibomian gland secretions via proteomic analysis (8,9).

The discovery of this molecule responsible for boundary lubrication at the ocular surface supports the hypothesis of Ehlers, who already in 1965 theorized that boundary lubrication must take place between the eyelid wiper region and the cornea (10). While a normal tear film containing mucins in the aqueous layer surely contributes to the normal hydrodynamic lubrication of the ocular surface, in pathologies such as dry eye disease where there is an altered tear film, boundary lubrication involving lubricin may be a primary method of friction reduction. Boundary lubrication may also be dominant at the cornea-contact lens interface where there is a relative lack of aqueous tear (5, 6, 8-11).

Therefore, the absence of lubricin may also promote ocular surface damage. Supporting this hypothesis, a higher fluorescein staining of the ocular surface has been demonstrated in animal models lacking lubricin. Since increased fluorescein staining is commonly associated with dry eye disease, a reduction in lubricin content may likely increase shear stress at the ocular surface, which, in turn may lead to inflammation and accumulation of inflammatory mediators in the tear film, triggering the typical symptoms of discomfort observed in dry eye patients. Supporting these hypothesis, the team of Sullivan and Schmidt (8) has recently described that the use of exogenous lubricin at the ocular surface provides a dramatic friction-lowering effect at the cornea-eyelid interface. Furthermore, given the known ability of lubricin to reduce friction on articular cartilage in a synergistic manner with hyaluronic acid, the current mainstay in dry eye symptoms' relief, and the broad commercial availability of ophthalmic formulations containing hyaluronic acid intended to provide lubrication, lubricin may also function synergistically with hyaluronic acid to reduce friction at the ocular surface.

Based on the available preclinical studies lubricin may be an important barrier to the development of corneal and conjunctival epitheliopathies in dry eyes and its use as a novel lubricating and anti-adhesive eye drop is under investigation in this clinical investigation.

2.1.2 Preclinical Toxicology Profile

The following Biocompatibility studies have been performed so far:

LUBRICIN EYE DROPS has been tested for cytotoxicity by direct contact on BalbC 3T3 monolayer cells according to ISO 10993-5:2009 and resulted not cytotoxic.

Guinea-pig maximization test was performed according to ISO 10993-10:2010 in order to evaluate the possible sensitization effects of LUBRICIN EYE DROPS, according to these results the ID was considered not sensitizing

Ocular irritation test in rabbit was also performed according to ISO 10993-10:2010. Following ocular examination with ophthalmoscope after 1, 24, 48 and 72 hours, the test item resulted not irritant. Ocular examination included the assessment of cornea, iris and conjunctiva.

The compatibility of LUBRICIN EYE DROPS with soft contact lens was tested according to ISO 11981:2009. The results obtained proved that the ID exerts physical compatibility to soft contact lens according ISO 11981:2009

Overall the preclinical toxicity data obtained in vitro and in vivo tests indicate a low risk of adverse side effects in humans under the circumstances of the intended clinical plan.

2.1.3 Hyaluronic acid (HA)

Hyaluronic acid is a linear polysaccharide found in all living organisms and is a universal component of the extracellular matrix of body tissues where it is distributed ubiquitously in all tissues (12). It is a molecule with negative charges and can form in the presence of H₂O a highly viscous solution. HA is a glycosaminoglycan present in the human vitreous and is able to bind a large number of water molecules and, therefore, creating a twisting ribbon structure which in physiological structure may occupy a very large domain, this also allows a very high swelling factor, up to 10.000 (13). The chemical structure of HA is formed by units of D -glucuronic acid and N-acetylglucosamine and remains constant throughout the phylogenetic chain. This identity is largely used clinically because if injected or administered to human it eliminates theoretically all the possible risks of allergic reactions, which instead are potentially present in the use of non-human natural products, such as non- human collagen (14). From the industrial point of view HA can be obtained by extraction from animal tissue, usually cockscomb, for bacterial fermentation and recombinant biotechnology. Natural HA has a relatively short half-life (1-2 days) in all connective tissues except the vitreous body of the eye (15).

2.2. Manufacturers

Lubricin Eye Drops manufactured by Dompé farmaceutici s.p.a. [name]. Produced (bulk and masked packaging) by PPD (See Annex A – Lubricin eye drops -Instruction for the subjects).

Sodium hayluronate (HA) 0.18%: (Vismed®) multidose manufactured by PPD will supply the HA for the Clinical Investigation in masked packing. (See Annex B – Vismed® 0.18% - Instruction for the subjects).

2.3. Investigational Devices (ID)

2.3.1 Treatment Period (Investigational Medical Devices)

TEST: Lubricin 20 µg/ml or Lubricin 50 µg/ml : is aseptically filled multidose container, suitable for products for ocular instillation. Lubricin 20 µg/ml or Lubricin 50 µg/ml will be supplied for the Clinical Investigation in masked packing.

For additional details on *Lubricin* please refer to [Annex A](#).

A single multidose container will supply treatment for both weeks of treatment. Instructions for use will be provided to the subject during visit 1.

CONTROL: Sodium hyaluronate (HA) 0.18% eye drops (Vismed®) multidose, commercially available in Italy will be supplied for the Clinical Investigation in masked packing.

For additional details on Vismed® please refer to [Annex B](#).

A single multidose container will supply treatment for both weeks of treatment. Instructions for use will be provided to the subject during visit 2.

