 - e. not willing to use highly effective birth control measures, such as: Hormonal contraceptives – oral, implanted, transdermal, or injected and/or mechanical barrier methods – spermicide in conjunction with a barrier such as a condom or diaphragm or IUD during the entire course of and 30 days after the study treatment periods.

TEST Investigational Medical Device, Dosage and Mode of Administration:*Treatment period:*

Sterile isotonic aqueous solution for ocular administration containing Lubricin 20 $\mu\text{g}/\text{ml}$ eye drops solution or Lubricin 50 $\mu\text{g}/\text{ml}$. In all patients, both eyes will be treated, unless only one eye meets the eligibility criteria. If just one eye is treated, that will be the "Study/Primary eye". If both eyes are

treated, the worst one (highest VAS average score) should be chosen as "Study/Primary eye"; in the event average VAS score was equal in both eyes, right eye will be chosen as "Study/Primary eye". The investigator will administer the morning study dose on Day 1 then patients will self-administer the drops at home/site, as applicable.

Eligible patients will self-administer 1 drop of Lubricin 20 µg/ml or Lubricin 50µg/ml in the eye(s) which underwent refractive surgery three times a day (TID) approximately every 6h for 2 weeks.

No other ocular topical treatments allowed, including artificial tears/lubricants.

Follow-up period:

Follow-up period of 7 days, any ocular topical treatments allowed, including other artificial tears/lubricants as prescribed by the treating physician.

Duration of Investigational Device Treatment:

Treatment duration 14 days (2 weeks) ±2 days (maximum treatment duration 16 days).

Follow-up period of 7 days, any ocular topical treatments allowed, including other artificial tears/lubricants as prescribed by the treating physician.

REFERENCE Investigational Medical Device, Dosage and Mode of Administration

Treatment period:

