6. STUDY DESIGN

6.1. Clinical Study Design

6.1.1. Description and Justification of Study Design

This is a 2-week randomized (1:1:1), controlled, double-masked, parallel group study, to evaluate tolerability, safety permanence on the ocular surface and efficacy of two concentrations of Lubricin (20 and 50 µg/mL) eye drops versus sodium hyaluronate (HA) 0.18% eye drops (Vismed®) in patients with ocular discomfort following refractive surgery.

Enrolled subjects will be randomized at inclusion, 1:1:1 ratio to receive Lubricin 20 µg/ml eye drops solution or Lubricin 50 µg/ml eye drops solution or sodium hyaluronate (HA) 0.18% eye drops solution. Upon randomization and until the end of the treatment period, subjects will be required to not use topical ophthalmic medications except of the study treatments.

On the Day 1 Visit (Baseline visit) subjects will be dispensed of the study medication and instructed to self-administer at home three times a day approximately every 6 hours for 2 weeks. Subjects will be evaluated after 2 weeks of treatment and 1 week after end of treatment.

The subjects will be involved in the study for a maximum of 25 days from screening visit to last follow-up visit.

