6.1.3. Duration and Timing of the Variable Recording

A written informed consent will be obtained before any study assessment or procedure. Maximum study duration will be 25 days, including all study visits.

Each study subject will undergo to 3 visits.

The first subject first visit (FSFV) is defined as the 1st visit performed at the clinical site by the 1st enrolled subject. The last subject last visit (LSLV) is defined as the last visit performed at the clinical site (or the telephonic follow-up, if applicable) by the last subject, i.e. the last visit foreseen by the study protocol, independently of the fact that the subject is a completer or a withdrawn subject.

The following phases, visits and procedures will be performed:

➤ **Interventional phase**

- Visit 1 - Day 1
- Visit 2 - Day 15 ± 2.

➤ **Follow-up phase**

- Visit 3 - Final Visit follow-up - (Day 22±2) /ETV (Early Termination Visit) in case of early discontinuation, discontinued subjects will undergo an early termination visit (ETV).

The procedures/assessments details are summarized hereafter.

	Day	Procedures/Assessments

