Baseline - Visit 1	Day 1 30 minutes post-dose	
The following procedures will be performed:
 
 ➤ Assessment of ocular tolerability (Visual analogue scale, VAS: dryness, foreign body sensation, burning/stinging, itching, pain, stick feeling, blurred vision and photophobia) ➤ Tear collection for Lubricin dosing in the left eye ➤ The Investigator will deliver to the patients the investigational medical device for the treatment period (15±2 days)
At home	From Day 1 to Week 2± 2 Days Visit	
 ➤ Self-administration at home of the Investigational medical device TID approximately every 6h into the eligible eye(s)
Visit 2	Week 2 ± 2 Days (prior the morning dose)	
The following procedures will be performed before receiving the first eye drop treatment of the day:
 
 ➤ Review of current medical conditions (ocular and systemic: including External Ocular Examination) ➤ AE and concomitant medications ➤ Ocular examination in both eyes, consisting of the assessments detailed for the baseline visit (points 1-10), in the same order and with the same intervals ➤ Urine Pregnancy test (only female) ➤ At the completion of the pre-dose assessments, the investigator will administer the study product (morning dose) into the eligible eye(s)
Visit 2	Week 2 ± 2 Days 15 minutes post-dose	
The following procedures will be performed:
 
 ➤ Assessment of ocular tolerability (Visual analogue scale, VAS: dryness, foreign body sensation, burning/stinging, itching, pain, stick feeling, blurred vision and photophobia) ➤ Tear collection for Lubricin dosing in the right eye
Visit 2	Week 2 ± 2 Days 30 minutes post-dose	
The following procedures will be performed:
 
 ➤ Assessment of ocular tolerability (Visual analogue scale, VAS: dryness, foreign body sensation, burning/stinging, itching, pain, stick feeling, blurred vision and photophobia) 
Tear collection for Lubricin dosing in the left eye

	Day	Procedures/Assessments

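### As written, Protocol 2.3.1 has subjects receive instructions for use that 2.2, 2.5 and 2.9 identify as product-named annexes, in conflict with the stated masking; the Visit 2 timing for Vismed is very probably a slip

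*Protocol*

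**What the plan says.** Protocol 2.3.1 describes each product in turn. Under the Lubricin entry it says "Instructions for use will be provided to the subject during visit 1". Under the Vismed entry the matching sentence is "Instructions for use will be provided to the subject during visit 2". In both cases the subject is the recipient.

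Three other sections say where those instructions are:

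- Protocol 2.2 cites Annex A as "Lubricin eye drops -Instruction for the subjects" and Annex B as "Vismed® 0.18% - Instruction for the subjects".
- Protocol 2.5 refers to Annexes A and B for the instructions for use.
- Protocol 2.9 refers to the same two annexes for correct use of the test and control devices.

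Annex A is headed as the subject's instructions for Lubricin eye drops. Its visible Italian text presents itself as proposed wording for the leaflet to accompany the experimental device, and says the wording may change. Annex B is headed as the patient's instructions for Vismed. Its visible text names the product and its ingredient, sodium hyaluronate.

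On masking, Protocol 6.2.2 says the presentation of the control was chosen so that masking is complete. Protocol 6.4.3 relies on the double-masked technique against bias. SAP 6.5 says neither investigators nor subjects know the treatment.

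**The concern.** Two separate things look wrong.

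The first concerns masking. A subject who receives a leaflet naming Lubricin or Vismed knows which product is in use. The VAS for eight ocular symptoms is a primary endpoint, and the subject marks it (Protocol 6.4.1.2). The SANDE is a secondary endpoint, also marked by the subject (Protocol 6.4.1.1). Both are compared between treatments (SAP 8.11.1.1 and 8.11.4.5). Self-rated discomfort is the kind of outcome that knowledge of the product can shift, so these comparisons depend on the subject not knowing it.

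The second is an inconsistency. Section 2.3.1 gives the instructions at different visits in different arms, while the rest of the protocol gives all arms one schedule.

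**Working it through.** No figure in the plan needs to be reproduced. The check sets the passages side by side.

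**Do the cross-references lead to a product-named document in the subject's hands?**

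1. Protocol 2.3.1: instructions for use go to the subject.
2. Protocol 2.2, 2.5 and 2.9: the instructions are Annex A for Lubricin and Annex B for Vismed.
3. Annex headings: subject's instructions and patient's instructions, each with the product name.

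Taken literally, steps 1 to 3 give each subject a leaflet that names the product.

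**Does any stated masking measure break that chain?**

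- Protocol 2.2 and 2.3.1: masked packing of the products.
- Protocol 2.4: a coded batch on the containers.
- Protocol 2.5.1: label content, with name and strength listed only for open studies. Directions for use may refer to a leaflet, but need not.
- Protocol 16.2 and SAP 6.5: sealed code envelopes.
- Protocol 6.4.4: the site materials list contains no neutral instruction sheet and no product leaflet. It adds that the CRO will supply other documents.

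None of these says that the instructions are masked, replaced by a common text or withheld from subjects.

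**Which contrasts could be exposed?** Three arms give 3 × 2 / 2 = 3 pairwise contrasts. Two of them compare a Lubricin arm with Vismed. The third, 20 versus 50 µg/mL, involves two arms that share Annex A, and nothing visible there separates the strengths.

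**Is Visit 2 for Vismed credible?**

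- Protocol 1.2 (flow chart): dispensing at Visit 1 only.
- Protocol 6.1.1: on Day 1 all subjects receive the product and are "instructed to self-administer at home three times a day approximately every 6 hours for 2 weeks".
- Protocol 6.1.3: the device is delivered 30 minutes after the Day 1 dose, and home dosing runs from Day 1 to the Week 2 visit.
- Protocol 11.3: test and control devices are both received at Visit 1.
- Protocol 6.1.3: "Visit 2 - Day 15 ± 2", which is Day 13 to Day 17. The synopsis gives a treatment duration of 14 ± 2 days, or 12 to 16 days.

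On the nominal schedule, Vismed instructions at Visit 2 would arrive when home dosing is over. Masked staff also could not apply a visit rule that depends on the arm. Both facts point to a drafting slip.

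**The case against.** The strongest reply turns the last argument round. If masked staff cannot time instructions by arm, they cannot choose between Annex A and Annex B either. The obvious remaining route is an insert inside the kit, and both products come in masked packing. Section 2.2 cites each annex right beside that masked supply, so masked packing can reasonably be read to cover the insert. Sections 2.5 and 2.9 only say where instructions are set out, which would suit reference material. Directions may instead be printed on the label, and the CRO may supply a neutral sheet. The body of Annex A and the Italian and English text of Annex B are not visible in the copy reviewed.

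Much of this stands. No section says that the annexes are given to subjects unaltered, and the intention to mask is plain. What it does not do is resolve the text. Sections 2.2 and 2.3.1 label the annexes as subject instructions and make the subject the recipient. No sentence extends masked packing to the leaflet. An insert in the kit would also reach the subject without any choice by staff.

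A reader might infer that the trial was in fact unmasked. The documents do not support that, because they describe a procedure and do not record what was handed over. A reader might also infer that Vismed subjects use the product without guidance until the end of treatment. Protocol 4.6 and 6.1.1 provide training and instruction in all arms, and the Visit 2 rule could not be carried out under masking. Counting 20 Lubricin subjects instructed on Day 1 against 10 Vismed subjects instructed about two weeks later therefore measures a probable slip and shows no imbalance.

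**Conclusion.** The concern holds as a conflict in the written procedure. Followed as written, 2.3.1 with 2.2, 2.5 and 2.9 would reveal Lubricin-versus-Vismed allocation to the people who mark the VAS and the SANDE, contrary to Protocol 6.2.2 and 6.4.3 and SAP 6.5. It is not evidence that anyone was unmasked.

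The size of any bias cannot be derived from the documents. If product-named leaflets reached subjects, which is an assumption, 2 of the 3 pairwise contrasts would be exposed. The comparison of the two Lubricin strengths is not shown to be affected.

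The Visit 2 wording is a separate point. It is very probably a slip and carries little weight beyond the need to reconcile the sections.

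SAP 8.3 calls the trial exploratory, with no regulatory claim resting on it. What is at stake is how far the preliminary comparisons with Vismed can be trusted. That places the point between minor and should-fix.

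**What to change.** - Reconcile the visit in Protocol 2.3.1 with 1.2, 6.1.1, 6.1.3 and 11.3.
- State in 2.2, 2.3.1, 2.5 and 2.9 that every subject receives the same product-neutral instruction sheet at the same visit, identified only by study code and kit number.
- List that sheet in 6.4.4. If a neutral sheet already exists, attach it and say so. If masked packing already removes or replaces the leaflet, say that too.
- Mark Annexes A and B as reference texts that are not given to subjects.

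The cost is one sheet and a wording amendment. Under Protocol section 9 the amendment must be written, justified, signed by the parties and sent to the Ethics Committee and the Competent Authorities. Sample size and analysis do not change.

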2.9. Methods and Medical Procedures in the Use of ID

The methods and the medical procedures for a correct use of the Test ID/Control ID are reported in detail in the “Instruction for Use” ([Annexes A and B](#)).

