ANNEX A

LUBRICIN EYE DROPS SUBJECT'S INSTRUCTIONS (Italian version)

FOGLIO ILLUSTRATIVO

LUBRICIN GOCCE OCULARI

Questo documento contiene il testo proposto da Dompé per il foglio illustrativo da utilizzare con il dispositivo medico (DM) sperimentale “Lubricina gocce oculari”. Al termine della valutazione ai fini della sperimentazione clinica, tale testo potrebbe subire delle modifiche.

Si fa anche presente che il nome “Lubricina gocce oculari” non sarà quello proposto per la marcatura CE, ma sarà solo utilizzato per identificare il DM stesso durante la sperimentazione clinica.

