ANNEX B

VISMED® PATIENT'S INSTRUCTIONS (Italian & English version)

Précautions: Ne pas toucher l'embout du flacon ouvert et ne pas toucher la partie de l'œil avec l'embout du flacon. Reposer le capuchon immédiatement après utilisation. Ne pas utiliser VISMED® MULTI si la lotion est échauffée. VISMED® MULTI peut être utilisée jusqu'à 3 mois après la première utilisation. A conserver entre 2 °C et 25 °C. Ne pas utiliser VISMED® MULTI après la date de péremption indiquée sur le flacon et la boîte. Si les troubles persistent, pendant l'utilisation de VISMED® MULTI, consulter un médecin.

Propriétés et mode d'action: VISMED® MULTI contient du hyaluronate de sodium, un polymère naturel également présent dans les structures de tissus humains. Les caractéristiques physiques particulières du hyaluronate de sodium contribuent à VISMED® MULTI ses propriétés viscoélastiques et de rétention d'eau. VISMED® MULTI forme ainsi un film stabilisant la surface de l'œil qui n'arrête pas l'irrigation d'eau minérale par le basculement des paupières. VISMED® MULTI offre ainsi un effet protecteur à un contre-irrigation. En raison de sa composition particulière, VISMED® MULTI est très bien tolérée.

Présentation: 10 ml de solution en flacon multiusage.

Dernière révision: Mars 2011

Contraindicaciones: Hypersensibilidad individual a alguno de los componentes del producto.

Interacciones: No utilizar VISMED® MULTI al mismo tiempo que otros medicamentos o productos aplicados al ojo que puedan modificar sus efectos.

Reacciones adversas: En muy raras ocasiones pueden aparecer reacciones de irritación de la conjuntiva, sensación de quemazón en los ojos, así como dolor, formación a corto plazo.

Posología y forma de administración: Abre el frasco de seguridad antes de la primera aplicación. Retira la tapa posterior. Inhala la cabeza hacia atrás, coloca la parte delantera sobre el ojo que atrae la lágrima, aplica al palpebral inferior con un ojo de los dedos indicados. Retira el ojo y coloca con firmeza una gota de VISMED® MULTI (una sola gota). Administrar. Si no se recomienda lo contrario, instila 1 o 2 gotas de VISMED® MULTI en el ojo tanto veces como sea necesario. Debes de posponer la solución se dispensaré formando una capa transparente y duradera en la superficie del ojo. VISMED® MULTI también puede usarse con lentes de contacto (gafas oftálmicas).

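### The protocol designates product-named, arm-specific leaflets (Lubricin; VISMED) as the subjects' instructions for use in a double-masked trial, and no visible masking measure covers them

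*Protocol*

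**What the plan says.** Protocol 2.2 gives each product its own instruction text and says who it is for: "See Annex A – Lubricin eye drops -Instruction for the subjects" and "See Annex B – Vismed® 0.18% - Instruction for the subjects". Section 2.5 states that the instructions for use are in Annexes A and B, and 2.9 sends the reader to the same annexes: "The methods and the medical procedures for a correct use of the Test ID/Control ID are reported in detail".

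Section 2.3.1 covers the handover. For Lubricin: "Instructions for use will be provided to the subject during visit 1". For the control: "Instructions for use will be provided to the subject during visit 2".

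Both annex titles address the subject or patient and name the product. The preamble of Annex A says the text is the sponsor's proposal and may be modified. It adds that the name given there for the Lubricin drops is not the one planned for CE marking but "sarà solo utilizzato per identificare il DM stesso durante la sperimentazione clinica". The readable part of Annex B is a VISMED MULTI product leaflet with a March 2011 revision date, and it names the product throughout.

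On masking, SAP 6.5 states that neither investigators nor subjects know the treatment, and Protocol 6.2.2 says the control's presentation was chosen to make masking complete.

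**The concern.** A masked bottle protects allocation only if nothing that comes with it names the contents. A subject given a leaflet headed Lubricin or VISMED knows whether the drops are the new product or the marketed comparator. One of the two primary outcomes is a set of symptom scores that subjects mark themselves on a 100 mm VAS, and an outcome of that kind is open to expectation. The other, treatment-emergent adverse events, depends partly on what subjects choose to report. The plan itself treats knowledge of allocation as serious: Protocol 16.2 restricts opening a code envelope to emergencies and removes from the trial any subject whose envelope is opened early.

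**Working it through.** No arithmetic applies. The check sets the relevant sections side by side.

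1. **Are instructions to be given to subjects?** Yes. Section 2.3.1 says so for the test and control products alike.

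2. **Which text are those instructions?** The handover sentences in 2.3.1 cite no annex. Section 2.5 fills the gap by identifying the instructions for use as Annex A (Lubricin) and Annex B (Vismed). Section 2.2 and both annex titles describe these as the subjects' or patient's instructions. No other instruction text appears in the visible documents.

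3. **Do those texts reveal the product?** Yes, by title and by readable content. The visible part of Annex A gives no strength, and 2.3.1 cites it for both concentrations. What would be revealed is therefore Lubricin (20 subjects planned) versus control (10 planned), not 20 versus 50 µg/mL.

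4. **Does any visible masking measure reach the instructions?**
   - 2.2 and 2.3.1: masked packing.
   - 2.4: coded batch on the containers.
   - 6.2.2: presentation of the control.
   - 2.5.1: the label. Item (b) calls for the product name or identifier only in open studies, so a masked label need not carry it. Item (g) lets the directions for use refer to a leaflet or other document meant for the subject. A masked label can therefore point to a leaflet that names the product.
   - 6.4.4: the list of site materials has no masked instruction sheet, although it leaves other documents to the CRO.

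5. **Is the difference in visit real?** Section 6.1.3 has the product handed over at Visit 1: "The Investigator will deliver to the patients the investigational medical device for the treatment period". Section 6.1.1 has all subjects, without distinction of arm, told on Day 1 to use the drops three times a day. Visit 2 closes the treatment period. Visit 2 for the control is therefore a slip for Visit 1. Correcting it does not affect steps 1 to 4.

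**The case against.** The strongest reply is that no sentence says the annex texts go to subjects unaltered. Section 2.3.1 cites the annexes only for further detail, 2.5 and 2.9 may simply tell the protocol reader where use is described, Annex A is openly provisional, and 2.5.1 gives a route for directions on a label that need not name the product. A masked sheet may well exist outside the visible text. This stands as a reason to keep the point small. It does not remove it: 2.2 says in terms that the annexes are for the subjects, and the label route can lead back to a leaflet.

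Two stronger readings are tempting, and the documents do not support either.

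- **Control subjects dose for two weeks without instructions, or the investigator can tell the arm from the visit at which instructions are given.** A reader might infer this from 2.3.1. The Day 1 dispensing and instruction in 6.1.3 and 6.1.1 contradict it. Any count of doses taken before Visit 2 would measure a typing error.

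- **Control subjects would follow a looser regimen than Lubricin subjects.** A reader might infer this from the leaflet's default: "Si no se recomienda lo contrario, instila 1 o 2 gotas de VISMED® MULTI en el ojo tanto veces como sea necesario". That sentence is Spanish text in an annex titled as Italian and English, at a single Italian site, and it gives way to other advice. The study supplies that advice through the Day 1 instruction (6.1.1), patient training (4.6) and the compliance check with deviation questions (11.3). Annex A's posology is not visible, so no difference between arms is shown.

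**Conclusion.** The concern holds as a minor point of masking and document alignment. As written, the protocol makes product-named, arm-specific leaflets the subjects' instructions for use, and following it would conflict with SAP 6.5 and with the complete masking claimed in Protocol 6.2.2.

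In principle it reaches all 30 planned subjects, since each would receive one of the two leaflets. The effect on VAS scores or adverse event reports cannot be quantified from the documents, and even its direction is unknown.

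The conclusion assumes that the annexes, or texts that name the product in the same way, are what subjects receive. If a masked sheet is already in use, what remains is a missing reference and a wrong visit number. SAP 8.3 describes the trial as exploratory with no regulatory claim resting on it, which also limits the consequence.

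**What to change.** Use one masked instruction sheet, identical in all three arms, that names no product, is given at Visit 1 and states 1 drop three times a day, about every 6 hours. Cite it in 2.2, 2.3.1, 2.5 and 2.9 in place of Annexes A and B as the subjects' instructions; the annexes can stay as reference material for the investigator's brochure and ethics file. In 2.3.1, change visit 2 to visit 1 for the control.

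The cost is one sheet, short edits to four sections and an ethics notification; the design, sample size and analysis are unaffected. If a masked sheet already exists, citing it and correcting the visit number is enough. SAP 6.4 describes allocation in the past tense, so for subjects already treated the clinical investigation report should state which instruction text they received.
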